7. PLANNED ANALYSIS

In general, the two trial parts (SRD and MRD) will be evaluated separately if not stated otherwise.

Safety analysis (refer to [Section 7.8](#)) will be performed by [REDACTED] and will be presented in Sections 15.1 to 15.4 of the CTR and in Appendix 16.2 and 16.1.13.1.

Inferential statistical analyses of PK endpoints (refer to [Section 7.5.2](#)) will also be performed by [REDACTED] and will be presented in Section 15.5 of the CTR and in Appendix 16.1.13.3.

Descriptive data analysis of PK parameters and concentrations will be performed by the department [REDACTED] and will be presented in Section 15.6 of the CTR.

Descriptive data analysis of gene expression data will also be performed by the department [REDACTED]

[REDACTED]

Descriptive data analysis of the efficacy endpoints will be performed by [REDACTED] and will be presented in Section 15.2 of the CTR and in Appendix 16.2.6.

The format of the listings and tables will follow the BI standards (see BI-KMED-BDS-HTG-0045 ([6](#)) with the exception of those generated for PK-calculations ([7](#))).

The individual values of all patients will be listed, sorted by dose group, patient number, and visit.

The listings will be included in Appendix 16.2 of the CTR.

For end-of-text tables, the set of summary statistics for non-PK parameters is:

N	number non-missing observations
Mean	arithmetic mean
SD	standard deviation
Min	minimum
Median	median
Max	maximum

For analyte concentrations and PK parameters, the following descriptive statistics will additionally be calculated:

CV	arithmetic coefficient of variation
----	-------------------------------------

gMean	geometric mean
gCV	geometric coefficient of variation
P10	10th percentile
Q1	1st quartile
Q3	3rd quartile
P90	90th percentile

The data format for descriptive statistics of concentrations will be identical with the data format of the respective concentrations. The descriptive statistics of PK parameters will be calculated using the individual values with the number of decimal places as provided by the evaluation program. Then the individual values as well as the descriptive statistics will be reported with three significant digits in the CTR.

Tabulations of frequencies for categorical data will include all possible categories and will display the number of observations in a category, as well as the percentage (%) for each dose group. Percentages will be rounded to one decimal place and will be based on all patients in the respective subject set whether they have non-missing values or not. The category 'missing' will be displayed only if there are actually missing values.

Units of variables should be given in the titles or column/row descriptors in square brackets (e.g. [mg]).

Exclusion of PK parameters

The ADS ADPP (PK parameters) contains column variables APEXC and APEXCO indicating inclusion/exclusion (APEXC) of a PK parameter and an analysis flag comment (APEXCO). All analyses based on the PKS will include parameters if they are not flagged for exclusion, that is APEXC is equal to "Included".

Exclusion of PK concentrations

The ADS ADPC (PK concentrations per time-point or per time-interval) contains column variables ACEXC or ACEXCO indicating inclusion/exclusion (ACEXC) of a concentration and an analysis flag comment (ACEXCO). Exclusion of a concentration depends on the analysis flag comment ACEXCO. For example, if ACEXCO is set to 'ALL CALC', the value will be excluded for all types of analyses based on concentrations. If ACEXCO is set to 'DESC STATS', the value will be excluded from descriptive evaluations per planned time point/time interval. If ACEXCO contains the addition 'TIME VIOLATION' or 'TIME DEVIATION', the value can be used for further analyses based on actual times. If ACEXCO is set to 'HALF LIFE', the value will be excluded from half-life calculation (and, as a consequence, any calculation that relies on λ_z) only; the value is included for all other analyses.

Further details are given in 001-MCS-36-472_RD-01 "Noncompartmental Pharmacokinetic / Pharmacodynamic Analyses of Clinical Studies" ([5](#)) and 001-MCS-36-472_RD-03 "Description of Analytical Transfer Files and PK/PD Data Files" ([11](#)).

7.1 DEMOGRAPHIC AND OTHER BASELINE CHARACTERISTICS

Only descriptive statistics are planned for this section of the report, based on the TS.

The data will be summarised by dose group and in total.

7.2 CONCOMITANT DISEASES AND MEDICATION

Frequency tables are planned for this section of the report, based on the TS.

Concomitant diseases will be coded using the latest version of the coding system of the Medical Dictionary for Drug Regulatory Activities (MedDRA). Medications will be coded using the latest version of the World Health Organization Drug Dictionary (WHO-DD). The coding version number will be displayed as a footnote in the respective output.

The diagnoses and medications will be listed. Patients without any concomitant diagnoses or concomitant therapies should be marked with a “No” in the respective column.

The relevance of the concomitant therapies to the evaluation of PK/biomarker analysis will be decided no later than at the RPM/DBLM.

7.3 TREATMENT COMPLIANCE

Section 4.3 of the CTP: *Compliance will be assured by administration of all trial medication in the study centre under supervision of the investigating physician or a designee. The measured sample concentrations will provide additional confirmation of compliance.*

It is not intended to list the compliance separately. Any deviations from complete intake will be addressed in the RPM/DBLM (cf. TSAP [Section 6.2](#)) and described in the CTR.

7.4 PRIMARY ENDPOINT

Refer to TSAP [Section 7.8](#) for a description of the analysis of safety and tolerability of BI 894416.

7.5 SECONDARY ENDPOINTS

7.5.1 Key secondary endpoints

This section is not applicable as no key secondary endpoint has been specified in the protocol.

7.5.2 Secondary endpoints

Primary analyses:

Section 7.3.2 of the CTP:

[figure not shown]
The secondary efficacy endpoints (refer to [Section 5.2.2](#) and [Section 5.4](#)) will be analysed descriptively based on the TS.

[figure not shown]
Boxplots by time-point and treatment group will be provided (for absolute values and changes from baseline).

[figure not shown]
Airway resistance includes 'Total airways resistance', 'Total specific airways resistance', 'Effective airway resistance' and 'Effective specific airway resistance'.

[figure not shown]
The secondary PK endpoints (refer to [Section 5.2.2](#)) will be analysed descriptively based on the PKS. Analyses will be performed for the parent drug.

[figure not shown]
Further exploratory analyses:

7.7 EXTENT OF EXPOSURE

Descriptive statistics are planned for this section of the report based on the TS. The date and time of drug administration will be listed for each patient.

7.8 SAFETY ANALYSIS

All safety analyses will be performed on the TS.

If not stated otherwise, the safety results will be sorted by dose group.

The safety data for treated patients who failed to complete the study (dropouts or withdrawals) will be reported as far as their data are available. All withdrawals will be documented and the reason for withdrawal recorded.

7.8.1 Adverse Events

AEs will be coded with the most recent version of MedDRA.

The analyses of AEs will be descriptive in nature and will be based on BI standards as presented in “Analysis and Presentation of Adverse Event Data from Clinical Trials – Display Template” [BI-KMED-BDS-HTG-0041] ([8](#)).

The standard AE analyses will be based on the number of patients with AEs (and not on the number of AEs).

The analysis of AEs will be based on the concept of treatment emergent AEs. That means that all AEs will be assigned to 'screening', 'on treatment' or 'follow-up' phases as defined in Section 6.1. AEs will be analysed based on actual treatments, as defined in Table 6.1: 1 and Table 6.1: 2.

According to the clinical study protocol, adverse events of special interest (AESI) will be analysed:

Section 5.2.6.1.4 of the CTP: *The following are considered as AESIs:*

- **Hepatic injury**
A hepatic injury is defined by the following alterations of hepatic laboratory parameters:
 - *an elevation of AST (Aspartate Aminotransferase) and/or ALT (Alanine Aminotransferase) ≥ 3 -fold ULN combined with an elevation of total bilirubin ≥ 2 -fold ULN measured in the same blood sample, or*
 - *aminotransferase (ALT, and/or AST) elevations ≥ 10 fold ULN*

These lab findings constitute a hepatic injury alert and the patients showing these lab abnormalities need to be followed up according to the 'DILI checklist' provided in the ISF. In case of clinical symptoms of hepatic injury (icterus, unexplained encephalopathy, unexplained coagulopathy, right upper quadrant abdominal pain, etc.) without lab results (ALT, AST, total bilirubin) available, the Investigator should make sure that these parameters are analysed, if necessary in an unscheduled blood test. Should the results meet the criteria of hepatic injury alert, the procedures described in the DILI checklist should be followed.

According to ICH E3 (9), in addition to Deaths and Serious Adverse Events, 'other significant' AEs need to be listed in the clinical trial report. These will be any non-serious adverse event that led to an action taken with study drug (e.g. discontinuation or dose reduced or interrupted).

An overall summary of AEs (including number of patients with any AE, drug related AEs, AESIs, serious AEs and drug related serious AEs) will be presented.

The frequency of patients with AEs will be summarized by treatment, primary system organ class (SOC) and preferred term (PT). Separate tables will be provided for patients with serious AEs, for patients with drug-related AEs, for patients with drug related serious adverse events and for patients with AESIs. In addition, the frequency of subjects with AEs will be summarised by treatment, worst intensity, primary system organ class (SOC) and preferred term (PT).

The SOC and PTs will be sorted by frequency (within SOC). The MedDRA version number will be displayed as a footnote in the respective output.

In addition, frequencies of patients with non-serious AEs that had an incidence of $> 5\%$ for at least one treatment will be summarised by treatment, primary SOC and PT.

For disclosure of adverse events on EudraCT additional information not included in a standard AE analysis will be performed. The following three entries will be created:

- Adverse Events per arm for disclosure on EudraCT
- Non-serious Adverse Events for disclosure on EudraCT
- Serious Adverse Events for disclosure on EudraCT

7.8.2 Laboratory data

The analyses of laboratory data will be descriptive in nature and will be based on BI standards [BI-KMED-BDS-HTG-0042] ([10](#)). In addition to the standard descriptive tables, line graphs (mean values and standard deviation over time) of absolute values, changes from baseline and percent changes from baseline will be provided for the normalised laboratory parameters.

Laboratory data will be analysed qualitatively via comparison of laboratory data to their reference ranges. Values outside the reference range as well as values defined as possible clinically significant will be flagged in the data listings.

Clinically relevant findings in laboratory data will be reported as adverse events if judged clinically relevant by the investigator, and will be analysed as such.

It is the investigator's responsibility to decide whether a lab value is clinically significant abnormal or not (at the RPM/DBLM at the latest).

Descriptive statistics of laboratory data including change from baseline will be calculated by visit based on the worst value of the patient at that visit.

7.8.3 Vital signs

Descriptive statistics over time including change from baseline will be performed for vital signs (blood pressure and pulse rate).

7.8.4 ECG

Continuous ECG monitoring (SRD part only)

Clinically relevant abnormal findings will be reported as adverse events.

No separate listing or analysis of continuous ECG monitoring will be prepared.

Continuous safety ECG monitoring (by investigator)

Clinically relevant abnormal findings will be reported as adverse events.

No separate listing or analysis of continuous ECG monitoring will be prepared.

12-lead ECG

Abnormal findings will be reported as baseline conditions (at screening) or as AEs (during the trial) if judged clinically relevant by the investigator.

The descriptive evaluations of ECG data will be based on the TS.

Listing of individual data

For all quantitative endpoints, listings of individual data will be shown in Appendix 16.2. For QTcB and RR only listings will be provided. Occurrences of notable findings will be flagged.

Comments regarding the ECGs will be listed.

Categorical endpoints

For the categorical endpoints, frequency tables will be provided.

For all patients with any notable finding in ECG intervals, a separate listing will be created as end-of-text display (based on the same display template as in Appendix 16.2), and the corresponding time profiles will be shown.

Quantitative endpoints

Descriptive statistics (N, mean, SD, min, median, max) will be provided for the changes from baseline over time of QTcF, QT, HR, PR and QRS. The time profiles of mean and SD for the changes from baseline on treatment will be displayed graphically by treatment.

For QTcF and HR changes from baseline, the relationship to the corresponding plasma concentrations will be evaluated using a random coefficient model. For patients in the ECGPCS, all time points with available ECG endpoints and valid time-matched drug plasma concentrations will be included. For the handling of missing values, see [Section 6.6](#).

The response variable will be the change from baseline in QTcF (Δ QTcF). The placebo patients will be included in the analysis, setting their plasma concentrations to zero.

As a first step, it is investigated if there is a potential delayed or accelerated (e.g. due to metabolites) effect of the drug on QTcF. A general visual impression is provided by overlaying time profiles of plasma concentrations and QTcF changes from baseline (Δ QTcF). These figures will be generated for each patient (presented in Statistical Appendix of the CTR), as well as for means per active treatment (presented in the End-of-Text part of the CTR).

The relationship between BI 894416 plasma concentrations and QTcF changes from baseline will be investigated in an exploratory manner using a random coefficient model to estimate the difference in means between BI 894416 and placebo of QTcF change from baseline and its 90% confidence interval at the geometric mean of the C_{\max} (SRD part) / $C_{\max,ss}$ (MRD part) for each dose. Additionally, the estimated overall slope with its 90% confidence interval will be provided. The used random coefficient model is based on a white paper from Garnett et al. ([12](#)) with Δ QTcF as response variable, centered baseline QTc and plasma concentration as

continuous covariates, treatment and time as fixed categorical effects, and a random intercept and slope for each patient. For more details refer to [Section 9.3](#).

For visualization, a scatterplot of the BI 894416 plasma concentration against the following individual QTcF values will be provided: For each patient on active treatment and each time point, subtract the mean value of all individual observed Δ QTcF values from the placebo group for this time point from the individual observed Δ QTcF value for this patient and time point. This results in estimates for “individual $\Delta\Delta$ QTcF” values, which should only be used for plotting purposes. The corresponding regression line and its pointwise confidence bands as well as and the geometric mean of C_{max} (SRD part) / $C_{max,ss}$ (MRD part) for each dose will additionally be displayed in the plot.

To check model assumptions, the conditional residuals will be plotted and presented in the Statistical Appendix of the CTR. In case of non-linearity or if there is evidence for a delayed effect, further models will be explored in order to better characterise the PK-ECG relationship (e.g. effect compartment models, non-linear models, etc.).

All of the above described graphical and statistical analyses will be also performed for HR in place of QTcF.

Appropriateness of heart rate correction methods of QT interval

To evaluate the appropriateness of the heart rate correction methods, the slope of the relationship of QTcF interval versus RR interval (values log-transformed using the natural logarithm) will be estimated by applying the random coefficient model described in [Section 9.1](#) using all time points. A scatterplot of QTcF vs RR including the overall regression line will be included in the Statistical Appendix of the CTR. The resulting (fixed effect) slope together with two-sided 95% confidence intervals will be included in the footnote for this plot.

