Visit	Day	Planned time (relative to BI 894416 or placebo administration [h:min])	Approximate clock time of actual day [h:min]	Event and comment	Safety laboratory ⁶	PK _{blood} ^{8,9,10}	PD _{blood} assay ^{8,9}	[REDACTED]	Physical Examination ⁹	Neurological examination ⁹	Vital signs (BP, PR) ^{9,12}	12-lead ECG ^{9,10}	Continuous ECG monitoring	Questioning for AEs and concomitant therapy ¹⁶	
1	-28 to -3			Screening (SCR) ¹	A ⁷			[REDACTED]	X ¹⁷	X	X	X			
2	-3 to -1	-72:00	08:00	Ambulatory visit ²	B ²			[REDACTED]		X		X ¹³		X	
3	1	-3:00	06:00	Admission, treatment allocation	C ⁷	X	X	[REDACTED]	X	X	X	X ¹⁴	X ¹⁵	X	
		0:00	08:00	BI 894416 or placebo administration ³				[REDACTED]					▲		
		0:15	08:15			X		[REDACTED]							
		0:30	08:30			X		[REDACTED]		X	X ¹⁴			X	
		0:45	08:45			X		[REDACTED]		X				X	
		1:00	09:00			X		[REDACTED]		X	X ¹⁴			X	
		1:30	09:30			X		[REDACTED]		X	X ¹⁴				
		2:00	10:00	240 mL fluid intake		X	X	[REDACTED]		X	X ¹⁴			X	
		2:30	10:30			X		[REDACTED]		X	X ¹⁴				
		3:00	11:00			X		[REDACTED]		X	X ¹⁴			X	
		4:00	12:00	240 mL fluid intake, thereafter lunch ⁴	B	X	X	[REDACTED]	X	X	X ¹⁴	▼		X	
		6:00	14:00			X		[REDACTED]		X	X ¹⁴			X	
		8:00	16:00	Snack (voluntary) ⁴		X	X	[REDACTED]		X	X ¹⁴			X	
		10:00	18:00			X		[REDACTED]							
		11:00	19:00	Dinner				[REDACTED]							
		12:00	20:00			X		[REDACTED]		X	X ¹⁴			X	
	2	24:00	08:00	Breakfast ⁴	C	X	X	[REDACTED]	X	X	X ¹⁴			X	
3		28:00	12:00	Lunch ⁴				[REDACTED]						X	
3		32:00	16:00	Snack (voluntary)				[REDACTED]							
3		34:00	18:00	Discharge from trial site		X		[REDACTED]		X	X			X	
4	3	48:00	08:00	Ambulatory visit	B	X		[REDACTED]	X	X	X			X	
5	4	72:00	08:00	Ambulatory visit		X		[REDACTED]		X	X			X	
6	5	96:00	08:00	Ambulatory visit		X		[REDACTED]						X	
7	8	168:00	08:00	Ambulatory visit	C			[REDACTED]	X					X	
8	15 to 17			Final Follow Up Visit ⁵	C			[REDACTED]	X	X	X	X		X	

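### The SAP's first look for a delayed QTcF or heart-rate effect has no placebo reference, so a meal or time-of-day change shared with placebo can resemble or mask a delay, mainly at low exposure

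*SAP*

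**What the plan says.** SAP 7.8.4 (Quantitative endpoints) opens the exposure-response work with a first step in which "it is investigated if there is a potential delayed or accelerated (e.g. due to metabolites) effect of the drug on QTcF". The tool is a visual impression from "overlaying time profiles of plasma concentrations and QTcF changes from baseline". On who is shown, it says: "These figures will be generated for each patient (presented in Statistical Appendix of the CTR), as well as for means per active treatment". Neither placebo subtraction nor a placebo curve is specified for these figures.

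The consequence comes later in the same section, directly after the sentence on plotting conditional residuals: "In case of non-linearity or if there is evidence for a delayed effect, further models will be explored", with effect compartment and non-linear models as examples. Heart rate is treated identically: "All of the above described graphical and statistical analyses will be also performed for HR in place of QTcF".

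Elsewhere SAP 7.8.4 does correct for placebo. The random coefficient model includes placebo patients at zero concentration, with treatment and time as categorical effects. The concentration scatterplot uses individual ΔΔQTcF values, obtained by subtracting the placebo mean at the same time point.

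Baseline (SAP 6.7) is a pre-dose value before the first administration, not one matched for time of day. In the SRD time schedule the 4 h entry reads "240 mL fluid intake, thereafter lunch". On MRD Days 1 and 9 lunch is 5 h after the morning dose. In both parts the next centrally read ECGs are at 6, 8 and 12 h.

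**The concern.** The plotted change at time t is the drug effect at t plus whatever placebo patients also show at t. The step asks about the drug, and the planned figure cannot separate the two parts. With a terminal half-life of 2.96 to 5.31 h (Protocol 1.2.2), concentrations are well past their peak by 6-12 h. A shared rise in that window is out of phase with concentration and has the shape of a delay. A shared fall can flatten a real one.

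The placebo-corrected scatterplot does not fill the gap, because it has no time axis. What is at stake is the judgement that the direct-effect model is adequate and, through it, whether further exploratory models are fitted. Protocol 1.4.3.1 already reports a possible concentration-dependent QTcF increase, so that judgement deserves a clean display.

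**Working it through.** The documents state no false-signal rate for this check, so there is no plan figure to reproduce. The calculation below shows how far a shared shift can distort the mean figure. It is not the error rate of any procedure in the SAP.

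**Inputs from the documents**
- 8 active patients per dose group. Pooled placebo is 2 × 3 = 6 in SRD (75, 125 and 170 mg run) and 2 × 4 = 8 in MRD (10, 25, 50 and 60 mg t.i.d. run; SAP 6.1).
- Observed gMean Cmax: 1,290 nM (50 mg t.i.d.), 2,340 nM (75 mg), 4,128 nM (125 mg), 5,280 nM (170 mg) (Protocol 4.1.2).
- Earlier trial: 5.9 ms placebo- and baseline-corrected QTcF increase at the 70 mg gMean Cmax (Protocol 1.4.3.1).

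**Assumptions**
- Cmax at 70 mg is not given. Scaling the 75 mg values by 70/75 gives 1,861 × 70/75 = 1,737 nM (predicted) and 2,340 × 70/75 = 2,184 nM (observed). The slope is then 5.9/2.184 = 2.7 to 5.9/1.737 = 3.4 ms per 1,000 nM; midpoint 3.05.
- One-compartment profile, ka 1.5/h, half-life 4 h, direct effect, no true delay. Carry-over from earlier t.i.d. doses is ignored.
- SD of the change at each time 8 ms, independent across times. Shared shift S of 3, 5 or 8 ms at 6, 8 and 12 h, equal in active and placebo.

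**Formulas**
- Concentration relative to peak averages 0.961 over 1, 1.5, 2 and 2.5 h and 0.364 over 6, 8 and 12 h. True early-minus-late gap = (0.961 − 0.364) × peak effect = 0.597 × peak effect.
- Uncorrected SE of the late-minus-early difference = 8 × √[(1/8)(1/4 + 1/3)] = 2.16 ms.
- Placebo-corrected SE = 8 × √[(1/8 + 1/n placebo)(1/4 + 1/3)] = 3.30 ms (SRD) or 3.06 ms (MRD).
- P(late mean ≥ early mean): uncorrected Φ[(S − gap)/2.16]; corrected Φ[−gap/SE], whatever S is.

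| Dose | Peak effect (ms) | Gap (ms) | Uncorrected, S = 3 / 5 / 8 ms | Corrected |
|---|---|---|---|---|
| 50 mg t.i.d. | 3.05 × 1.290 = 3.9 | 2.35 | 62% / 89% / >99% | 22% |
| 75 mg | 3.05 × 2.340 = 7.1 | 4.26 | 28% / 63% / 96% | 10% |
| 125 mg | 3.05 × 4.128 = 12.6 | 7.52 | 2% / 12% / 59% | 1% |
| 170 mg | 3.05 × 5.280 = 16.1 | 9.61 | <1% / 2% / 23% | <1% |

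Simulation gives about 64% for the 75 mg entry at 5 ms. At 5 ms, moving the slope from 2.7 to 3.4 changes the four entries to 91-86%, 71-55%, 22-6% and 5% to <1%. Moving the SD from 6 to 10 ms changes them to 95-84%, 68-61%, 6-18% and <1% to 4%.

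**Cross-check on another measure** (simulation, 8 active against 6 placebo, ka 2/h, direct 6 ms effect, shared rise of 5 ms at 6 h tapering to 70% at 8 h and 50% at 12 h, SD 6-8 ms). The uncorrected mean profile peaks at 6 h or later in 44-52% of replicates, the corrected one in 7-11%.

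**Masking.** A truly delayed 6 ms effect (assumed effect-compartment rate 0.3/h) shows 6.0 ms at 6 h. A shared fall of 5 ms leaves 6.0 − 5 = 1.0 ms there. The 4 h value stays at 6.0 ms, so the delay is obscured rather than removed.

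**The case against.** The strongest reply is that little hangs on this figure. The SAP calls it a general visual impression and attaches no test or threshold. The sentence on further models follows the conditional-residual check, and those residuals come from a model that already removes time effects shared with placebo. Mean change profiles are also displayed by treatment, so a placebo shift would be visible. Further models are added to characterise the relationship better; nothing says the prespecified model is dropped. The whole analysis is exploratory. SAP 9.3, cited for model details, is not in the text available for this review and might say more.

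Most of this stands and limits the point. It does not remove it. The by-treatment profiles carry no concentrations, neither they nor the residuals are named as the basis for judging a delay, and no criterion defines evidence of one. The step named for that purpose is the one without a placebo reference.

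Three stronger readings are tempting and not supported:
- That the estimated QTcF effect is biased. It is not, for the reason given by the model's placebo and time terms.
- That a stated share of trials would falsely declare a delay. That needs a formal early-versus-late test, which the SAP does not contain.
- That all figures show active patients only. This is exact for the mean figures; the individual ones are for each patient and may include placebo patients, though they remain uncorrected.

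**Conclusion.** The point holds as a limited weakness in a diagnostic display. A shared meal or time-of-day change can resemble or mask a delay in the planned overlays and so influence whether further exploratory models are fitted.

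The risk is concentrated at low exposure. A 5 ms shared shift exceeds the early-to-late gap expected at 50 mg t.i.d. (2.35 ms) and slightly exceeds that at 75 mg (4.26 ms), but falls short of the gaps at 125 and 170 mg (7.52 and 9.61 ms). A shared artefact would therefore fade as dose rises.

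The size of the shift, the SD, the absorption rate and the 70 mg Cmax are assumptions. The documents give no placebo change for QTcF or heart rate, and the heart-rate case has not been sized.

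**What to change.** In SAP 7.8.4, change the mean overlay to show, against mean concentration, the mean change on each active dose minus the pooled placebo mean change at the same planned time (ΔΔQTcF and ΔΔHR), with confidence intervals. At the least, add the pooled placebo change profile to the same figure. State that any conclusion about a delayed effect rests on this figure together with the conditional residuals. Keep the uncorrected individual overlays as supplementary figures.

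This needs SAP wording and re-use of a placebo subtraction already defined for the scatterplot; no new data are required. The price is noise. The SE of each plotted mean rises by √(1 + 8/6) = 1.53 in SRD and √(1 + 8/8) = 1.41 in MRD, that is from 2.8 to 4.3 or 4.0 ms at an SD of 8 ms. With no shared shift, the chance that the late mean reaches the early mean at 50 mg t.i.d. rises from about 15% to 22%. Because one placebo mean is subtracted from every dose, a chance dip in 6 or 8 placebo patients appears in all curves. The confidence intervals, and keeping the uncorrected overlays alongside, guard against over-reading that.
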